Mini International Neuropsychiatric Interview (M.I.N.I.): The M.I.N.I. (Sheehan et al., 2006) is a semi-structured diagnostic assessment of DSM-5 psychiatric illnesses. The M.I.N.I. is efficient, reliable, and well-validated.

Assessment of OCD and Related Symptoms

Yale-Brown Obsessive Compulsive Scale (Y-BOCS): The Yale-Brown Obsessive Compulsive Scale (Y-BOCS); Goodman, Price, Rasmussen, & Mazure, 1989) is a 10-item, clinician-administered measure of OCD symptom severity, which will be our primary outcome

measure. The Y-BOCS assesses individuals' obsessions and compulsions on a scale ranging from 0-4. At the screening visit, clinicians will administer a checklist to preliminary assess which obsessions and compulsions are present.

Obsessive Compulsive Symptoms Rating Scale (OCSRS): The OCSRS ([name] & Steketee, 2006) is a self-report measure of the severity of specific OCD symptom domains.

Clinical Global Impression – Improvement Scale (CGI-I) and severity scale (CGI-S) (Appendix): This rating scale, which ranges from 1 (very much improved) to 7 (very much worse), is commonly used in clinical trials (Guy, 1976). Participants will complete a CGI for OCD symptoms (CGI-P OCD) and the clinician will complete a CGI for OCD symptoms (CGI-OCD) and overall symptoms (CGI-global). The CGI will be a secondary outcome measure and will also be used to determine clinical deterioration of OCD (see Minimizing Risks, below). The CGI also has a severity scale (CGI-S) which is rated by the clinician at baseline. The CGI-S determines the patient's level of severity, in comparison to others the clinician has treated or assessed with the same diagnosis.

Patient Health Questionnaire-2 (PHQ-2) (Appendix): The PHQ-2 (Kroenke & Spitzer, 2002) self-report measure of depression severity includes 2 Likert scale items ranging from 0 (*not at all*) to 3 (*every day*). The 2 items are taken from the longer PHQ-9 measure and are selected because they assess the core diagnostic symptoms of depression. The PHQ-2 will be administered weekly via the app (or REDCap for those in the control condition) to monitor changes in depression symptom severity.³

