Quick Inventory of Depressive Symptomatology- Self Report (QIDS-SR) (Appendix): The QIDS-SR (Rush et al., 2003) is a self-report measure of depressive symptoms consisting of 16 scale items with responses ranging from 0 to 3, including one suicide item (item #12). Higher scores correspond with greater depression severity, and the measure is well-validated, sensitive measure of symptom severity in depression. The response choices on the suicide item include 0: "I do not think of suicide or death"; 1: "I feel that life is empty or wonder if it's worth living"; 2: I think of suicide or death several times a week for several minutes"; and 3: "I think of suicide or death several times a day in some detail, or I have made specific plans for suicide or have actually tried to take my life". The QIDS-SR will be used to determine eligibility at the baseline screening visit and to assess depressive symptoms at subsequent assessment visits.

Suicide item (Appendix): A question assessing the presence and nature of suicidal thoughts will be delivered weekly to participants via the app (or REDCap for those in the control condition) to monitor for risk concerns during the trial. Scores >0 will trigger a popup message to the participant about calling 988 or 911/going to the ER and will provide information about contacting a suicide hotline. Scores >1 will also trigger a text message alert to the clinician with the specific item response given by the participant (e.g., 2 vs. 3). The clinician will follow up with the participant within 24 hours by phone to assess for risk, and to refer to a higher level of care if clinically indicated (see Minimizing Risks, below).

Columbia-Suicide Severity Rating Scale (C-SSRS) (Appendix): The C-SSRS (Posner et al., 2010) is a gold-standard, clinician-administered assessment of suicidal ideation and suicide

behaviors. The baseline version, which assesses both lifetime and recent time frames, will be used to establish eligibility at the baseline/screening visit. The “Update” version, which assesses suicide risk since the last assessment, will be used at subsequent study administrations.

Assessment of Functioning and Quality of Life

Work and Social Adjustment Scale (Appendix): The WSAS is a self-report measure of impairment in occupational, social, and family domains (Mundt et al., 2002).

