Form Type	Data Collection Method	Measure	Baseline	Baseline Re-assess	Weekly	Week 4	Mid-Treatment Assess (wk 6)	Post-Treatment Assess (wk 12)	3-month Follow-up	12-month Follow-up
Diagnosis & Screening	Paper/PDF/REDCap	MINI	x							
	REDCap	Demographics	x							
	REDCap	Treatment History	x							
	REDCap	Treatment History	x							
	REDCap	Treatment History	x							
	REDCap	Lifetime Meds	x							
OCD & Related Symptoms	Paper/PDF/REDCap	Y-BOCS	x	x			x	x	x	x
	REDCap	OCSRS	x				x	x	x	x
	REDCap	QIDS-SR	x	x			x	x	x	x
	App/ REDCap	PHQ-2			x					
	App/ REDCap	Suicide item			x					
	REDCap	C-SSRS: Lifetime	x							
	REDCap	C-SSRS: Update		x						
	REDCap	CGI-S: Clinician	x	x						
	REDCap	CGI-I: Clinician		x			x	x	x	x
Functioning	App/ REDCap	CGI-I: Patient (OCD)			x			x	x	x
	REDCap	Q-LES-Q	x				x	x	x	x
Safety	REDCap	WSAS	x				x	x	x	x
	REDCap	CONCOM		x			x	x	x	x
	REDCap	Adverse Events Form		x			x	x	x	x
Tx expectancy, motivation,	REDCap	Life Events		x			x	x	x	x
	REDCap	Cred/Expectancy	x				x			
	REDCap	CSQ-8					x	x		
	REDCap	URICA	x							

Form Type	Data Collection Method	Measure	Baseline	Baseline Re-assess	Weekly	Week 4	Mid-Treatment Assess (wk 6)	Post-Treatment Assess (wk 12)	3-month Follow-up	12-month Follow-up
satisfaction, feedback	REDCap	TUQ - App†	x				x	x	x	
	REDCap	TUQ – Website*	x				x	x	x	
	REDCap	App Feedback†	x				x	x		
	REDCap	Website Feedback*						x		
	REDCap	Technologist							x	
	REDCap	uMARS†						x		
Neurocognitive	REDCap/Inquist	Stroop	x			x		x		
	REDCap/Inquist	WCST	x			x		x		
COVID	REDCap	COVID Impact	x				x	x	x	x
	REDCap	GAD-7 with COVID	x				x	x	x	x
	REDCap	Substance Use	x				x	x	x	x
Other	Beiwe	Wifi check-in question			x					
	REDCap	Self-Help Questionnaire	x				x	x	x	x

† Only included for participants in the CBT app condition

* Only included for participants in the HealthWatch condition

If more than ten days elapse between a patient's initial baseline screening assessment and the start of treatment, the study IE would re-administer select forms, including an additional Y-BOCS and QIDS-SR form.

Despite our best efforts to retain participants, we do expect dropouts. Except for subjects who withdraw consent to participate, all who are withdrawn or drop out of the study will be asked to complete all scheduled assessments and we will provide renumeration for participation in assessments

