Phone Usage Patterns: Dynamics of the phone usage provides an additional insight into clinically relevant changes to a person's mental health status. For that reason, Beiwe will collect phone-unlock events and data traffic to characterize patterns and quantify daily phone and internet usage. Note that the data traffic refers only to the periodically sampled number of bytes sent and received, and it does not include any sensitive information such as internet history or the names of the installed applications. Beiwe may also monitor how much the participant uses their phone for calling and texting and keep track of the people they communicate with. To encourage occasional interaction with the Beiwe app, we will administer a weekly survey question to participants via Beiwe (Wifi check-in question). For details on how this information will be stored and anonymized please see "Privacy and Confidentiality" below.

However, sampling raw GPS location coordinates may intrude on one's privacy. To protect privacy of the study participants, we will apply the following procedure. The location coordinates will be first collected at the secured server located at the hospital or locally on the phone. We will subsequently remove the raw location coordinates by replacing them with randomly generated strings as location labels (such as "ghhu45", "235oh4", "8n8hj3", ...), where each unique location in the dataset will correspond to a unique de-identified label. This will allow us to quantify mobility of the participants without requiring us to store actual geographical locations in the long-term. In addition to location, other sensor data collected by the participant's Smartphone may be used to quantify mobility, including accelerometer, steps, calories burnt, and sedentary time.

Application Usage Metrics: To improve the usability of the application, usage metrics may be collected (for example operating system version and device model, time and date when the application is opened or closed, time spent on each page visited, notification timing, etc). Additionally, we may collect user's battery status and charging patterns, and network traffic (e.g., number of bytes sent/received, and the hashed Wi-Fi-antenna indicator). These metrics will be stored in the same fashion as passive sensor data and user survey responses collected via the app.

B. Drugs to be used

Not applicable

C. Devices to be used

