We will use the same hierarchical mixed modeling approach as described for the primary endpoint to examine significant differences in secondary outcome measures (i.e., depression severity (H2.1), functional impairment (H2.2), and quality of life (H2.3)) at post-treatment between participant in the app-CBT vs. supportive attentional control conditions. We will not adjust for multiple testing among secondary outcomes based on the recommendation of Cook and Farewell (1996), who argue that multiplicity adjustments are not necessary if separate test results are interpreted marginally and address different aspects of the patient experience and decision-making process rather than alternative assessments of efficacy.

Exploratory endpoint 1: Assess feasibility and acceptability

Analysis:

We will test feasibility and acceptability by examining:

- H3.1: Refusal and dropout rates and reasons, by group: Drop-out rates by treatment (app-CBT vs. supportive attentional control) will be compared using logistic regression. Drop-outs will be defined operationally as participants who do not complete either an endpoint or follow-up assessment of the primary outcome measures (Y-BOCS), as well as participants in the CBT arm who do not use the app or participants in the HealthWatch arm who do not use the website at least once between assessments (i.e., at least once between baseline and week 6 and at least once between week 6 and week 12). We will use one-tailed tests to examine if the odds of drop-out in the app-CBT group are higher; if non-significant, we will interpret the results as an indication that the app-CBT treatment is feasible in comparison to the supportive attentional control condition; conversely, significantly higher odds of drop-out in the app-CBT condition would indicate a lack of feasibility.

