We will use hierarchical mixed models similar to the ones used for the primary and secondary outcome analyses, but will add follow-up assessments (i.e., 3-month and 12-month) to the data as additional time-points. We will then use specific contrasts (for each outcome model) to test for significant treatment group differences at the 12-month follow-up time-point. In the case that at least 10% of the participants who completed the end-of-treatment assessment initiated additional or subsequent evidence-based treatment for OCD at clinically relevant dosage (for medication) or frequency (for therapy), we will conduct a sensitivity analysis for this aim using treatment (yes/no) as a time-varying covariate in the model to account for the potential effect of outside treatment. In this context, ‘evidence-based’ treatments will be operationally defined to include any psychosocial or medication treatments indicated for OCD or closely related anxiety disorders that have shown efficacy in prior clinical trials, and ‘clinically relevant dosage’ will be evaluated by psychiatrists or psychologists in our treatment program who specialize in OCD or related disorders. In addition, we will also add descriptive stats about how many participants are responders at both end-of-treatment and 12-month follow-up, how many participants are new responders by the 12-month follow-up, how many participants are no longer considered responders at the 12-month follow-up, and how many participants were not considered responders at either assessment. No formal comparisons will be made between treatments in these numbers.

Exploratory endpoint 3: Treatment utilization for OCD concerns following the 3-month follow-up.

Analysis:

We will use logistic regression analysis to examine whether the likelihood of seeking further treatment for OCD during the treatment or follow-up phases (overall, combined) differs between participants who were assigned to the app-CBT and those assigned to the supportive attentional control condition. For this analysis, we will operationally define “treatment utilization” as any indication of participants seeking treatment for OCD during or following the treatment phase, regardless of whether the treatments sought are pharmacological or therapy-based, at sufficient or insufficient dosage/frequency, or considered evidence-based or not.

D. Power analysis

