
4) Technologist data: Computerized data and digital audio files collected from feedback interviews with technologists will be stored de-identified, in password protected files in the Partners Healthcare Dropbox Business folder. The PHS Dropbox Business folder will be set up by a listed owner with a Partners email address. Per Partners Research Information Services and Computing, “The enterprise rollout of Dropbox Business at Partners HealthCare is an approved storage and collaboration solution. This version of Dropbox Business provides unlimited storage, fully encrypted data (AES-256 encrypted) and is compliant with Partners’ policies and procedures. Dropbox Business allows you to sync, share, and manage your files online” (<https://rc.partners.org/kb/article/2285>).

5a) Data collected through the app: All intervention app data will be sent from the participant's mobile client device to the clinical study server via an Internet connection secured by SSL. The clinical study server will be located in the PHS/MGH Secure Data Centers and hosted on PHS managed infrastructure. The collected data will be linked to the study identifier only (described in "1" above). Participants will be advised to avoid identifying themselves in answers to free response questions. The administrative interface to the clinical study server (channels 1 and 5 below) will be password protected with access limited to study staff. To further minimize risk the administrative interface of the clinical study server will only be available over the PHS network.

5b) Data collected through the control site: Interactions between participant's client device and the control condition site will occur over the Internet using secured by SSL to secure the data in transit. The control site will be hosted on the MGH OCD Programs commercial WordPress account. The only data persisted in the control condition site will be the anonymous study identifier, the survey week identifier, and confirmation of survey completion. Although surveys are presented for participants to complete the actual answers are not part of the evaluation and thus they are not saved for analysis in the control condition to minimize inadvertent disclosure risk. The control site will be password protected to limit access to study staff.

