
[figure not shown]
The RA responsible for data entry will inspect each form completed by the IE and the study participant within 1-3 business days of the assessment; if required data elements in IE completed forms are missing, the RA will contact the IE to complete the missing items. If participant-completed surveys are missing key variables (i.e., basic demographics, ratings used to evaluate safety based on suicidal ideation or symptom worsening), the RA will contact the participant by email or phone to obtain the missing data.

[figure not shown]
The data manager or an RA trained in data management tasks will run reports of the available REDCap data summarizing aggregate accrual and retention information, adverse events, protocol deviations, and inter-rater reliability ratings to track protocol adherence and check data quality with the RA responsible for data entry. These reports will be run on a weekly or biweekly basis. The PI and Sub-Investigators will review these reports once a month. In addition, the data manager will run monthly systematic data checks of the REDCap databases to check for inconsistent data values, missing data fields, missing forms, and study visits conducted out of window. Any failed data checks will be brought to the attention of the RA responsible for data entry, who will resolve them in REDCap within 1-14 business days. Changes made to the REDCap source documentation will be tracked within REDCap through data history logs that keep timestamps, user-IDs, as well as past and new data entered in an automated audit trail.

[figure not shown]
Figures 2-14-. Data flow and storage chart – Overview and Breakdown of App Data

[figure not shown]

[figure not shown]

De-identified data collected by the study's Beiwe app will be stored in a guarded, restricted-access Amazon Web Service (AWS) account operated by a collaborator at the Harvard School of Public Health. AWS has released a whitepaper (attached) describing how EC2 and S3, the two Amazon services Beiwe uses, meet HIPAA compliance standards. Access to the AWS account on which data are stored is restricted and requires username and password. Participants may withdraw their data by notifying the PI in writing.

We anticipate that the above procedures will ensure the confidentiality and integrity of study data.

C. Ongoing Monitoring of Coaching Fidelity

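### Does leaving 'use' of the app or website undefined in H3.1 bias the drop-out comparison between arms?

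*Combined protocol and SAP*

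**What the plan says.** Section VI.C, Exploratory endpoint 1, H3.1 defines drop-out by two routes. One is failure to complete an endpoint or follow-up Y-BOCS. The other is non-use: "participants in the CBT arm who do not use the app or participants in the HealthWatch arm who do not use the website". One use is required in each of two windows, the first from baseline to week 6 and the second from week 6 to week 12. Drop-out is compared by logistic regression with a one-tailed test for higher odds in the app arm. A non-significant result is read as feasibility.

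Other sections bear on what could be recorded as use:

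- **App records.** Application Usage Metrics (Study Procedures, A) says that metrics may be collected to improve usability, including "time and date when the application is opened or closed".
- **Website records.** Privacy and Confidentiality, item 5b: "The only data persisted in the control condition site will be the anonymous study identifier, the survey week identifier, and confirmation of survey completion".
- **Weekly items.** Of the PHQ-2: "The PHQ-2 will be administered weekly via the app (or REDCap for those in the control condition"). Of the suicide item: "will be delivered weekly to participants via the app (or REDCap for those in the control condition"). Minimizing of Risks, item 5, splits the patient-rated CGI in the same way.
- **Self-report.** The Measures Chart schedules a Treatment Utilization Questionnaire (TUQ) in an app version (footnote: "Only included for participants in the CBT app condition") and a parallel website version. H3.1 names neither.

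**The concern.** H3.1 gives a platform, a minimum frequency and two windows, but no action and no data source. If the analyst turned to system records, the same behaviour could count in one arm only. A CBT participant who has abandoned the modules but still answers the weekly questions has opened the app. A HealthWatch participant who does the same has visited REDCap, not the website. Coach messaging shows the same split: inside the app for CBT, by email or telephone for HealthWatch. In the other direction, a HealthWatch participant who logs in and reads, but completes no survey, leaves no trace on the site.

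Section IX.B seemed to add to this. For missing key variables, including "ratings used to evaluate safety based on suicidal ideation or symptom worsening), the RA will contact the participant by email or phone", which might prompt an app opening by someone no longer in treatment. Exploratory endpoint 3 seemed to show that the authors could be more exact, since treatment utilization is defined there as "any indication of participants seeking treatment for OCD during or following the treatment phase".

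All of these differences would push the one-tailed test toward non-significance. At stake is a claim of feasibility that partly reflects how use was counted, or a definition settled after the data are seen.

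**Working it through.** **Is there a figure to reproduce?** H3.1 has none. The plan's one computed figure is the sample size for the primary endpoint. A two-sample t-test with difference 0.76, SD 1.1, two-sided alpha 0.05 and power 0.90 needs 45.006, so 46 per arm. Then 46/(1 − 0.20) = 57.5, so 58 per arm and 116 in all, as stated in VI.D. This confirms that the 20% drop-out is a planning allowance for the primary endpoint. It is not an estimate of H3.1's composite rate and serves below only as a base value.

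**What must hold for the bias to arise?** For app non-use to be under-counted, all four of these are needed:

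1. Logs are the source. H3.1 does not say so, and the app metrics only may be collected.
2. A bare opening or a weekly monitoring item counts as use. This is not stated anywhere.
3. The participant stops treatment yet keeps answering items in the app in each window.
4. The same participant still meets the Y-BOCS criterion; otherwise they are a drop-out by the first route.

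Hypothesis 3.1 in VI.B concerns drop-out from app-delivered CBT. Use therefore most naturally means use of the treatment, and condition 2 then fails.

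**Do the supporting passages carry weight?** IX.B has the research assistant obtain missing data by email or phone; it does not send anyone back into the app. The definition under Exploratory endpoint 3 names no form or data source either, so it is not a stricter standard that H3.1 falls short of.

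**How large could it be if any app contact counted?** Assumptions: 60 per arm (120 randomized, 1:1), control drop-out 20%, and k app non-users wrongly recorded as users, with k not derivable from the documents. The test is a one-sided Wald test on the log odds ratio at 0.05.

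With 12/60 control drop-outs:

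- 21/60 in the app arm: OR = (21/39)/(12/48) = 2.154, ln OR = 0.767, SE = √(1/21 + 1/39 + 1/12 + 1/48) = 0.421, z = 1.82, p = 0.034.
- 20/60 in the app arm: OR = 2.00, ln OR = 0.693, SE = 0.423, z = 1.64, p = 0.051.

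At this control count, one misrecorded participant changes the conclusion only if the true app count is exactly 21, and two only if it is 21 or 22.

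Exact enumeration of two independent binomials gives the chance of a non-significant (feasible) result. The app rates span VI.D's figures from low therapist contact to none:

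| True app drop-out | k = 0 | k = 1 | k = 2 |
|---|---|---|---|
| 20% | 0.950 | 0.968 | 0.980 |
| 25% | 0.841 | 0.884 | 0.919 |
| 30% | 0.653 | 0.721 | 0.782 |
| 35% | 0.427 | 0.502 | 0.578 |
| 40% | 0.225 | 0.286 | 0.354 |

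The first misrecorded participant adds 1.8 to 7.5 percentage points. The k = 0 column comes from the decision rule itself and owes nothing to how use is defined.

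**And if website use required a completed survey?** Let x be the share of otherwise retained HealthWatch participants who visit but submit no survey in some window. Apparent control drop-out becomes 0.20 + 0.80x: 24% at x = 5%, 28% at x = 10%. By a pooled two-proportion approximation, the chance of detecting a true 40% against 20% falls from 78% to 59% and 40%. This is a larger effect, but x is unknown, and the loss arises only if an analyst applies a strict rule to the website and not to the app.

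**The case for a change.** The strongest case for acting is that the gap is real, the possible errors run in one direction, and the repair is cheap. No section defines use; the split between app and REDCap is documented; and non-significance is the favourable outcome. A few sentences would settle the definition before data are seen. That the intended meaning seems obvious is not the same as stating it.

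Much of this stands. The definition is incomplete, and counting every app contact would be a poor choice. What does not follow is that the plan as written gives a wrong result. No stated rule does so; the harm needs an analyst to adopt a reading that fits the hypothesis less well.

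Nor is the obvious repair clearly better. The TUQ is scheduled in both arms, but it is self-report and measures time practising skills both on and off the platform. That suits a health-information website poorly, and the form is missing for anyone who skips week 6. Comparable content records are already described. App exercises are logged through the app and sent to the study server (Treatment Format; Privacy and Confidentiality, 5a), and HealthWatch survey completion is stored by week (5b). An analyst can count at least one module or exercise, or at least one module survey, in each window and leave out the monitoring items, without any amendment.

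**Conclusion.** No change follows. H3.1 leaves out a detail that a competent analyst would fill by reading use as engagement with treatment content in both arms, leaving out the weekly monitoring items and treating coach contact alike.

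The size of any bias cannot be derived. Under the any-contact reading, the illustration puts it at roughly 2 to 8 percentage points on the chance of a feasible conclusion for one misrecorded participant. That rests on 60 per arm, a 20% control rate borrowed from the power section, and an assumed number misrecorded. The website mechanism could be larger but needs unequal strictness between arms, which the plan does not call for.

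The endpoint is exploratory, and the primary and secondary efficacy analyses do not use this definition. Section VI also tabulates drop-out by reason and arm, and H3.3 plans descriptive statistics of app use, so disengaged app users could still be seen. The conclusion would change if the analysis were found to count bare app openings against completed website surveys.
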